5.4.2. Derivation of eDiary Assessment Times for Efficacy and Exploratory Analysis

There will be some scenarios whereby responses appear to have been limited by the diary programming if questions are not answered during the programmed window.

One specific scenario is missing dose timing data. If the dose is reported taken in the CRF but the subject is not able to select the date and time in the diary, then the date of dose will be missing in diary data. In such cases, efficacy assessments will be considered as missing. However, for safety analysis, the dosing date and time in the CRF will be considered as the baseline timing.

Unless otherwise specified, if incomplete data or contradictions are found for other reasons, then such data will not be used for analysis. Such irregular cases will be listed.

e.g. If meaningful pain free time is before dosing time, then it is contradiction. This data will not be used for the meaningful pain free time analysis.

e.g. If there are two data record at a specific timepoint, then first data record is used for that time point and the other one will be discarded. In addition, all data recorded at subsequent timepoints will be discarded.

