5.4.1. Handling of Missing Values

Subjects who fail to record information at an analysis time point will have that value considered missing in the respective table (hence, no imputation), unless otherwise specified.

Pain free, Pain relief, and MBS analysis are exceptions to this. Missing value at a particular time point is considered as “non-responder.”

Note that if a patient takes a rescue/recurrent medication at some postbaseline timepoint (see Section 5.4), then all evaluation after that timepoint becomes nonresponder, even if the evaluation is missing.

For time-to-event analyses (Time to Meaningful Pain Relief Through 48 Hours, Time to Pain Free Through 48 Hours), patients will be censored at the first time when rescue/recurrent medication are used or at 48 hours, whichever the earliest.

For the other time-to-event analyses (Kaplan-Meier analyses), the patient will be censored at the first missing evaluation time point or rescue/recurrent medication taken time (postbaseline), or the last possible evaluation point whichever the earliest, unless otherwise specified. For example, the last possible evaluation point of disability is at 24 hours.

A sensitivity analysis for missing data will be performed. (See Section 5.6.2).

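### SAP 5.4.2 discards every eDiary record after a duplicated time point without giving a reason, so a duplicate at 0.5, 1 or 1.5 h turns a recorded 2 h response into a non-response in [T1]-[T3]

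*SAP*

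**What the plan says.** SAP 5.4.2 deals with eDiary irregularities. It opens by noting that diary programming may have limited responses "if questions are not answered during the programmed window". It then gives three rules.

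- **Dose time missing from the diary:** "In such cases, efficacy assessments will be considered as missing".
- **Other incomplete or contradictory data:** "then such data will not be used for analysis". It adds: "Such irregular cases will be listed".
- **Two records at one time point**, given as an example of the preceding rule: "then first data record is used for that time point and the other one will be discarded". The next sentence extends this: "In addition, all data recorded at subsequent timepoints will be discarded".

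SAP 5.4.1 sets the general rule for absent values: "Subjects who fail to record information at an analysis time point will have that value considered missing in the respective table". Pain free, pain relief and MBS are exceptions: "Missing value at a particular time point is considered as" non-response.

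SAP 5.6.1 runs [T1], [T2] and [T3] on the mITT population. SAP 5.6.2 repeats these and the MBS analysis on ITT and PPS, and again on mITT after removing patients who are non-responders only because post-baseline data are missing. The SAP revision history says that the sentence on incomplete or contradictory data was updated to handle contradicting data. It says nothing about later time points.

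**The concern.** The discard reaches further than the rule it is meant to illustrate. That rule removes incomplete or contradictory data. A single 2 h entry made after a double entry at 1 h need be neither. The other example in the same section, a pain-free time earlier than dosing, drops only the faulty item, and only from the analysis of that item.

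The 0.5, 1 and 1.5 h assessments all precede the 2 h endpoint that carries the primary and both key secondary tests. A duplicate at any of the three deletes the 2 h value, and SAP 5.4.1 then scores it as failure. A patient who entered no pain at 2 h would be analysed as not pain free. An observed outcome would be replaced by an imputed one, and no planned analysis would show the result with the observed value.

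**Working it through.** **Which duplicates matter.** The postdose time points are 0.5, 1, 1.5, 2, 3, 4, 24 and 48 h. A duplicate at 0.5, 1 or 1.5 h deletes the 2 h value. A duplicate at 2 h does not, because the first 2 h record is kept.

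**Inputs (SAP 5.2), in the order placebo, 50, 100, 200 mg.**
- mITT patients: 190, 81, 190, 163 (total 624).
- Pain free at 2 h: 21.3, 28.6, 31.4, 38.8%.
- Pain relief at 2 h: 47.7, 59.0, 64.8, 65.0%.
- Two-sided alpha 0.05; pain free and pain relief independent, as the SAP assumes.

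**Plan's own power.** I simulated trials with Wald log-odds tests for [T1] and [T3] (without the preventive-medication covariate) and the Cochran-Armitage test with scores 0, 50, 100, 200 for [T2].

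| | [T1] | [T2] | [T3] | All three |
|---|---|---|---|---|
| SAP | 93.6% | 94.9% | 91.2% | 85.6% |
| Simulated | 95.1% | 94.9% | 92.3% | 86.8% |

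The joint figure is 1.2 points above the SAP's, close enough to compare scenarios.

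**Expected recorded responders.**
- Pain free: 190 × 0.213 + 81 × 0.286 + 190 × 0.314 + 163 × 0.388 = 40.5 + 23.2 + 59.7 + 63.2 ≈ 186.5.
- Pain relief: 190 × 0.477 + 81 × 0.590 + 190 × 0.648 + 163 × 0.650 = 90.6 + 47.8 + 123.1 + 106.0 ≈ 367.5.

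**Effect of the rule.** Let x be the share of patients with a duplicate at 0.5, 1 or 1.5 h. The documents give no value, so I assume 1, 2 or 5%, equal in all arms and unrelated to outcome; 5% is an upper illustration. Under SAP 5.4.1 each 2 h rate p becomes p(1 − x) with n unchanged. Recoded responders number x × 186.5 and x × 367.5. Without duplicates the [T1] difference is 38.8 − 21.3 = 17.5 points and the [T3] difference is 64.8 − 47.7 = 17.1 points; each is multiplied by (1 − x).

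| x | Patients affected (624x) | Pain free recoded | Pain relief recoded | [T1] difference | [T3] difference | Power, all three |
|---|---|---|---|---|---|---|
| 0 | 0 | 0 | 0 | 17.5 | 17.1 | 86.8% |
| 1% | 6 | 1.9 | 3.7 | 17.3 | 16.9 | 85.9% |
| 2% | 12 | 3.7 | 7.3 | 17.2 | 16.8 | 85.0% |
| 5% | 31 | 9.3 | 18.4 | 16.6 | 16.2 | 81.8% |

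**The planned SAP 5.6.2 exclusion.** Here the rates stay as they are and n becomes n(1− x), rounded: 188/80/188/161, 186/79/186/160 and 180/77/180/155. The differences return to 17.5 and 17.1 points, and joint power is 86.7, 86.2 and 84.3%. At 5%, exclusion alone costs 86.8 − 84.3 = 2.5 points. Recoding costs a further 84.3 − 81.8 = 2.5 points.

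**The case against.** The strongest reply is that the rule is prespecified and may be sound. It sits in a section about the limits of the diary programming, and SAP version 2 was approved before unblinding. If a double entry signals that the diary has lost its place, later records may be unreliable, and the documents do not show otherwise. The SAP also lists irregular cases and already plans an analysis without missing-data non-responders, which removes the dilution under equal rates. All of this stands, and it limits the weight of the point. It does not supply the reason for the discard, and the planned exclusion removes these patients instead of restoring what they recorded. The ITT and PPS repeats inherit the same discard.

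A reader might also infer that the SAP leaves the status of a discarded value open, so that two programmers could report different [T1]-[T3] rates, one counting these patients as failures and the other dropping them. SAP 5.4.1 does describe missing values as ones a subject failed to record, and SAP 5.4.2 says missing for an absent dose time but only discarded for duplicates. Even so, the documents do not support that inference. The non-responder rule does not depend on why a value is absent. Where the SAP means exclusion it says so, as for modified sustained pain freedom (5.6.3) and subgroup SUB21 (5.8). And SAP 5.6.2 makes exclusion a sensitivity analysis, which would change nothing for these patients if they had already left the primary one. Non-response is the governing reading; a clarifying sentence is still worthwhile.

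**Conclusion.** The point holds as a minor one. SAP 5.4.2, read with 5.4.1, can turn a recorded 2 h response into a non-response in the primary, both key secondary and the MBS analyses, for a reason the documents do not give, and no planned analysis uses the recorded value.

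At assumed rates of 1 or 2% the loss of joint power is about 1 or 2 points. At 1% it is smaller than the gap between my model and the SAP's figure. At 5% it is about 5 points. These sizes rest on assumed rates, equal across arms and unrelated to outcome.

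It would be going too far to infer that the rule favours lasmiditan: under equal rates it shrinks the treatment difference. Unequal rates could move the result either way. Under the same model, 5% in the 100 and 200 mg arms only would give 67.9% joint power, and 5% in placebo only would give 93.5%. Nothing in the documents points to such an imbalance.

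**What to change.** Before database lock, amend SAP 5.4.2 in one of two ways.

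1. **No device-related reason for the rule:** limit the discard to the second record at the duplicated time point. Keep later records unless they are themselves contradictory. Run the present discard rule as a sensitivity analysis of [T1]-[T3].
2. **A device-related reason to distrust later records:** state it in 5.4.2, keep the rule, and add a sensitivity analysis of [T1]-[T3] that uses the recorded 2 h value.

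In either case, say in 5.4.2 that a discarded value counts as missing under 5.4.1.

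The cost is a few SAP sentences, one extra sensitivity analysis and a check of a few diaries.

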5.5. Treatment Group Comparability

5.5.1. Patient Disposition

The following summary and listing will be created

Summary of Discontinuation Before Randomization

Reason for screen failure will be presented (by overall). Display count and percentage with respect to the screen failed patients.

Summary of Study Disposition

It is summarized by overall (total of PLA/LY50/LY100/LY200), by LY_ALL (total of LY50/LY100/LY200) and by treatment groups (PLA/LY50/LY100/LY200) as counts. The analysis population is all randomized patients/SP/ITT/mITT. The summary will be created for each analysis population separately. The summary will display the number of subjects in each category/sub-category/sub-sub-category. For both category and sub-categories, display count and percentage with respect to the number of subjects in the direct root category. (E.g. The direct root of a sub-sub-category is the sub-category.):

- Subjects who completed the study
 - Subjects who took study treatment
 - Subjects who did not take study treatment
 - ❖ Reasons for not treated (by treatment/overall).
- Subjects who discontinue the study
 - Reasons for the study discontinuation (including lost-to-follow-up).

Note 1: A patient who completes the study is one who is randomized and does not discontinue throughout the 8 weeks treatment period, regardless of study drug administration.

Note 2: All subjects who discontinue the study do not take study treatment.

Listing of Study Disposition

Disposition data and subjects who discontinue from the study will be presented per subjects for enrolled population

Summary of Analysis Population

The summary contains following counts. It is summarized by overall (total of PLA/LY50/LY100/LY200) and by treatment group (PLA/LY50/LY100/LY200) as counts.

- The number of screened patients. (all enrolled population)
- Subjects in each of the analysis population, all randomized population/ITT/mITT/SP/PPS (by treatment/overall). Display count and percentage with respect to all randomized population.

Listing of Analysis Population

For each patient, display Yes/No flags for Enrolled Population, all randomized population/ITT/mITT/SP/PPS.

In addition to the summary information, the listing contains “reasons for excluding from PPS”.

Summary of Patient Allocation by site

For each site, counts enrolled population/all randomized population/SP/ITT/mITT/PPS.

Listing of Study Disposition for COVID-19 related subjects

The listing for subjects who discontinued due to COVID=19 will be created for enrolled population.

5.5.2. Important Protocol Deviations

Listings of subjects with important protocol deviations will be provided for all randomized population. Important protocol deviations will be determined before unblinding. Detailed criteria and identification methods will be specified in separate document (Trial Issue Management Plan and individual patient record) which also specifies exclusion of PPS.

Summary of important protocol deviations will be created for all randomized population/ITT/mITT (by treatment/overall)

[mTOQ-6 Conversion Method 2] Convert responses as follows: Never (0 points); Rarely (0 points); Less than half the time (1 points); and Half the time or more (2 points). A total score from 0 to 8 is calculated by summing the points from 4 of the items (2-hour pain free, sustained 24-hour pain relief, comfortable to make plans, and perceived control) which define categories of acute treatment response: very poor (0), poor (1-5), moderate (6-7), and maximum (8) treatment efficacy (Lipton et al. 2015).

Note: If patient has missing response, then it will be excluded from the summary for that question.

- Summary of EQ-5D-5L of each question, index score and visual analog scale (Visit 2)
- Summary of Driving Assessment at Baseline:
 - Driving assessment (Yes/No)

Note: "Yes" means patient who has a driver's license at Visit 2. "No" means patient who does not.

- Involvement in any car accidents in past 6 months (yes and being the driver/otherwise)
- If anyone involved in that accident have to seek medical attention for injury
- If the subject has a migraine prior to or during the accident
- If the subject has taken any medications to treat his migraine prior to the accident
- Received any citations/tickets for any moving violations (Yes/No). If Yes, display the reason:
 - speeding violation,
 - failure to stop
 - disregarding traffic light
 - failure to signal
 - seat belt violation
 - cell phone related violation
 - violation of rules around school buses and school zone
 - falling asleep while driving
 - driving under the influence
 - other
- If the subject has a migraine prior to or during the traffic violation
- If the subject has taken any medications to treat his migraine prior to the violation
- Narrative for the car accident for all patients will be created as listing.

All demographic data above will be presented in a listing for safety population.

In addition, a detailed summary of triptan usage at baseline will be created. It is defined in "Triptan responder vs. insufficient responder (SUB1)" in Section [5.8](#).

5.5.3.1. Pre-Existing Conditions and Medical History

Medical history and pre-existing conditions will be coded using the Medical Dictionary for Regulatory Activities (MedDRA) with the latest version and sorted alphabetically by system organ class (SOC) and then preferred term (PT) by frequency. Subjects with multiple occurrences of the same medical history term will be counted once within the corresponding system organ class and preferred term. All pre-existing conditions and medical history will be presented in a listing.

5.5.4. Previous, Concomitant, and Post-Dose medications

The frequency and percentage of prior, concomitant, and post-dose medication use will be presented by treatment group.

- Prior medications are those taken (started) before study drug dosing.
- Concomitant medications are those taken within 48 hours (inclusive) after study drug dosing.
- Post-dose medications are those taken after 48 hours (exclusive) of study drug dosing and on or before the end of the study.

Prior/Concomitant medications/Post-dose are summarized in 3 groups:

- [1] Acute migraine treatments
- [2] Preventive migraine treatments
- [3] The other medications (medications which are not categorized in [1] nor [2])

These are presented by ATC4 medication class and WHO drug name. Medications will be coded using the WHO Drug Dictionary with the latest version and sorted by frequency of preferred name. [1] and [2] are defined in a separate EXCEL by medical review.

The descriptive statistics of the indications, the responses, and the discontinuation reasons will also be presented for prior medications [1] and [2] displayed by treatment and overall.

Listing of Migraine Treatments Used in the Past Three Months will be created for safety population.

5.5.5. Compliance

Treatment compliance will be assessed in terms of the actual dose. Treatment compliance will be used to characterize the patients and determine clinical evaluability for some analyses.

Treatment compliance will be summarized by descriptive statistics (counts for each category of treatment compliance=yes/no, and their percentage (%)) (by treatment/overall). This is based on Safety Population. If patients took all assigned dose (measured by the amount of returned tablet), then his compliance=yes. Otherwise his compliance=no.

The list of treatment compliance will be created (Dispense Date, # of tablets dispensed, Returned Date, # of tablets returned, compliance (%), lot number)

Electronic diary compliance (entered or missing) at each time point will be summarized (by treatment/overall)

The list of the eDiary compliance will be created.

5.5.6. Treatment Dosing

Summary of Migraine Onset and Dosing Times (frequency cross table) will be created by 6 treatment groups (PLA, LY50, LY100, LY200, LY_ALL, Overall).

Migraine onset time is categorized as midnight -3AM/3AM-6AM/6AM-9AM/9AM-Noon/Noon-3PM/3PM-6PM/6PM-9PM/9PM-Midnight/Total Dose time is categorized in the same way as the migraine onset time.

5.6. Efficacy Analyses

5.6.1. Primary and Key Secondary Analysis

The following statistical tests [T1] (primary), [T2] (key secondary), and [T3] (key secondary) will be conducted sequentially ([T1], [T2], then [T3]) by a gatekeeping method. This guarantees that the overall type 1 error across the set of primary and key secondary hypothesis tests is 0.05. Other assessments will not be part of the gatekeeping procedure.

- [T1] Primary: placebo vs. lasmiditan 200 mg (pain free at 2 hours) will be based on Wald's test by logistic regression.
- [T2] Key secondary: dose response of placebo, lasmiditan 50 mg, 100 mg, and 200 mg (pain free at 2 hours) will be based on Cochran-Armitage trend test.
- [T3] Key secondary: placebo vs. lasmiditan 100 mg (pain relief at 2 hours) will be based on Wald's test by logistic regression.

The analysis population for [T1], [T2], and [T3] under the gatekeeping procedure is the mITT.

When testing sequentially ([T1], [T2], and [T3]), if one of them becomes statistically non-significant, then all subsequent analyses will be conducted but will be designated as exploratory rather than confirmatory. That means, if [T1] is not significant, then [T2] and [T3] are exploratory. If [T1] is significant but not [T2], then [T3] is exploratory.

Note that regardless of the test results in [T1], [T2], and [T3], the other secondary and exploratory analysis are not adjusted in multiplicity (Section [5.6.4](#)).

For the [T1] analysis, the statistical test will be based on placebo vs. lasmiditan 200 mg using the logistic regression model that includes treatment (placebo, lasmiditan 50 mg, lasmiditan 100 mg, and lasmiditan 200 mg) and baseline usage of preventive medications to reduce the frequency of migraine (Yes/No).

For the [T2] analysis, the Cochran-Armitage trend test will be based on placebo, lasmiditan 50 mg, lasmiditan 100 mg, and lasmiditan 200 mg. The trend parameter is 0, 50, 100, and 200. This is to estimate the dose-response relationship of lasmiditan (dose zero to 200mg).

For the [T3] analysis, the statistical test will be based on placebo vs. lasmiditan 100 mg using the logistic regression model that includes treatment (placebo, lasmiditan 50 mg, lasmiditan 100 mg, and lasmiditan 200 mg) and baseline usage of preventive medications to reduce the frequency of migraine (Yes/No).

A sample SAS code for logistic regression is;

```
proc logistic data = myData;  
  class TRT(param=ref ref="PL") baseMedUse;  
  model AVAL(event='1') = TRT baseMedUse;  
  run;
```

To estimate the response rate for each arm, along with 95% confidence interval, least-square means (LSMeans) will be used.

Summary of Characteristics of Treated Migraine (at onset of dosing) will be created (mITT/SP).

Listing of Subject Efficacy Responses will be created.

